10.6.5 Electrocardiogram (ECG)

For Part A, ECGs will be collected in triplicate at all time points excluding screening and the last scheduled follow-up visit. These ECG data will be presented as below. For Parts B and C, ECGs will be presented if collected in triplicate. Otherwise, ECGs from Parts B and C will not be presented, and any clinically significant findings from ECGs will be reported as an AE.

The ECG data will be obtained directly from the 12-lead ECG traces. These data include the PR, QT, QRS duration and heart rate. In addition, QT interval corrected using Fridericia's formula (QTcF) will be calculated as follows:

$$QTcF = \frac{QT}{\sqrt[3]{60/HR}}$$

The ECG data will be summarized by part, treatment and time point together with changes from baseline, where baseline is defined as the mean of the triplicate Day 1 predose. Figures of mean ECG data and mean changes from baseline will be presented by part and treatment. The frequency of participants with a maximum increase from baseline in QTcF interval will be summarized by part, and for each treatment according to the following categories: >30 ms and >60 ms. In addition, the frequency of participants with QTcF postdose values, according to the following categories: >450 ms, >480 ms and >500 ms, will be summarized by treatment.

CONFIDENTIAL Protocol Reference: J4L-MC-KMAA

Concentration-QTc Analysis (Part A only)

A plasma LY3872386 concentration-QTc analysis will be performed to assess the relationship between changes from baseline (mean of Day 1 predose assessments) in QTcF (Δ QTcF) and plasma LY3872386 concentrations across all treatments. IV and SC data will be pooled.

A linear mixed effects analysis model will be employed with ΔQTcF as the response variable, time-matched LY3872386 concentration as the explanatory variable (0 for PBO), centered baseline QTcF as an additional covariate, treatment (PBO=0 or LY3872386 =1), PK profile day, time (nominal time postdose), and the interaction between PK profile day and time as fixed effects, and a random intercept and concentration slope per participant. The model⁴ will have the form:

$$\Delta ECG_{i,j,k,l} = (\theta_0 + \eta_{0,i}) + \theta_1 TRT_j + (\theta_2 + \eta_{2,i})C_{i,j,k,l} + \theta_{3,k} DAY_k + \theta_{4,l} HOUR_l + \theta_{5,k,l} DAY_k \times HOUR_l + \theta_6 (ECG_{i,j,k=1,l=0} - \overline{ECG_{k=1,l=0}}) + \varepsilon_{i,j,k,l},$$

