where $\Delta ECG_{i,j,k,l}$ is the change from baseline in QTcF parameter for participant i on treatment j (PBO, or LY3872386) on PK profile day k at l hours postdose. θ_0 is the population mean intercept in the absence of a treatment effect, $\eta_{0,i}$ is the random effect associated with the intercept term θ_0 , θ_1 is the fixed effect associated with the dichotomous treatment variable TRT_j , θ_2 is the population mean slope of the assumed linear association between concentration and ΔECG , $\eta_{2,i}$ is the random effect associated with the slope θ_2 , $C_{i,j,k,l}$ is the concentration for participant i on treatment j on PK profile day k at l hours postdose, $\theta_{3,k}$ is the fixed effect associated with categorical hours postdose l, $\theta_{5,k,l}$ is the fixed effect associated with the interaction term between PK profile day and hours postdose, θ_6 is the fixed effect associated with a participant's centered baseline QTcF value, $\overline{ECG_{k=1,l=0}}$ is the overall mean of $ECG_{i,j,k=1,l=0}$ (all participant's baseline QTcF parameter values, which are denoted as being on PK profile day 1 at hour postdose 0), and $\varepsilon_{i,j,k,l}$ is the residual error. It will be assumed the random effects are multivariate Gaussian distributed with mean vector $\mathbf{0}$ and an unstructured covariance matrix G, whereas the residuals, $\varepsilon_{i,j,k,l}$, are Gaussian distributed with mean 0 and variance r.

If this model fails to converge, the following covariance structures will be tested in order:

- Compound symmetry
- Variance components

The first covariance structure that converges will be used. If the model still fails to converge, the PK profile day-by-hour interaction term, followed by the random effects for slope, followed by intercept, will be removed until convergence is achieved. Other covariance structures may be considered if deemed appropriate.

The centered baseline QTcF will be derived as follows:

CONFIDENTIAL Protocol Reference: J4L-MC-KMAA

- Calculate the arithmetic mean of the triplicate QTcF parameter for each subject at each timepoint and use this in all subsequent calculations below.
- Calculate the overall baseline QTcF value, which is the mean of all participants' baseline QTcF values.
- For each participant, subtract the overall baseline QTcF value from their own individual baseline QTcF value. This will be each participant's centered baseline QTcF.

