For postdose concentrations that are below the quantifiable lower limit of the assay (BQL), the following will be applied:

- For the PBO arm, all LY3872386 concentrations will be imputed as 0.
- For the LY3872386 arms, BQL concentrations will be treated as missing without any imputation.

The LY3872386 concentration slope and corresponding 90% CI will be reported. The model will also be used to derive the predicted $\Delta QTcF$ and PBO-corrected $\Delta QTcF$ ($\Delta\Delta QTcF$) at the geometric mean C_{max} of each dose level (PBO=0) for the last PK profile day along with the corresponding 90% CIs in a tabular format.

All $\Delta QTcF$ versus time matched LY3872386 concentrations will be plotted, with PBO concentration set to zero. A linear regression line from the model above will be included on the plot along with the corresponding 90% CI.

Predicted $\Delta\Delta QTcF$ from the above model versus LY3872386 concentration will also be plotted. The plot will include a linear regression line from the model above, corresponding 90% CI, and reference lines at the geometric mean C_{max} for each dose.

To check the model covariates are adequate, a scatter plot will be produced plotting the residuals of the fitted model versus LY3872386 concentration. A locally estimated scatterplot smoothing curve with 95% CI will be fitted to aid with this assessment.

The hysteresis loop plot between mean $\Delta\Delta QTcF$ and geometric mean LY3872386 concentration will be generated through 24 hours postdose in a temporal order for each PK profile day, with all LY3872386 doses combined. If deemed appropriate, further timepoints may be included if 24 hours does not adequately encapsulate the hysteresis loop. Mean $\Delta\Delta QTcF$ will be derived by performing a 2-sample t-test at each time point independently, with the 2 groups consisting of PBO and the combined LY3872386 treatments.

Similar analysis will be conducted for RR, HR, PR, and QRS.

CONFIDENTIAL Protocol Reference: J4L-MC-KMAA

Examples of the SAS code that will be used are as follows:

```
proc mixed data=xxx alpha=0.1;
  by param;
  class trt(ref='0') time subjid;
  model ΔECG = basec trt day hour day*hour conc / cl alpha=0.1 ddfm=kr2
residual;
  random intercept conc / subject=subjid type=un;
  estimate 'PBO' intercept 1 trt 0 1 conc 0/ cl alpha=0.1;
  estimate 'Δ at XX mg' intercept 1 trt 1 0 conc [cmax] / cl alpha=0.1;
  estimate 'ΔΔ at XX mg' trt 1 -1 conc [cmax] / cl alpha=0.1;

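### If the unstructured fit fails, the concentration-QTc model falls back first on compound symmetry, which equates an intercept variance with a slope variance measured in different units

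*SAP*

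**What the plan says.** SAP 10.6.5 (Concentration-QTc Analysis, Part A only) models ΔQTcF on time-matched LY3872386 concentration with fixed effects for treatment, day, time, their interaction and centred baseline, "and a random intercept and concentration slope per participant". The random effects have mean zero "and an unstructured covariance matrix G"; the residuals have a single variance. The example SAS code holds both random effects in one statement, "random intercept conc / subject=subjid type=un", and has no REPEATED statement.

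The convergence rule follows directly: "If this model fails to converge, the following covariance structures will be tested in order". The first on the list is "Compound symmetry", the second is variance components, and "The first covariance structure that converges will be used". No comparison of fit is required. Only if neither converges are terms removed: the day-by-hour interaction, then the random slope, then the random intercept. A closing sentence adds: "Other covariance structures may be considered if deemed appropriate".

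On output, "The LY3872386 concentration slope and corresponding 90% CI will be reported", together with 90% intervals for predicted ΔQTcF and ΔΔQTcF at each dose's geometric mean Cmax, with placebo at concentration zero. A similar analysis is planned for RR, HR, PR and QRS. Concentration is not standardised and no unit is fixed for this model. The PK tables in SAP 10.3.1 use µg/mL, with a footnote that leaves units to the laboratory or to presentation preference.

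**The concern.** Compound symmetry suits repeated measurements of one quantity on one scale. Here it would be imposed on two quantities with different dimensions. Equality of their variances has no scientific meaning, and whether it is roughly true depends on the unit in which concentration is recorded. Because the rule takes the first structure that converges, variance components, which does not have this problem, would never be reached if compound symmetry converged. The reported slope, ΔQTcF and ΔΔQTcF intervals would then come from a model that can badly misstate how participants vary.

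**Working it through.** **Which matrix the list governs.** The list follows the statement on G, the residuals have one variance, and the code has a single RANDOM statement. The structures therefore apply to the 2×2 matrix G.

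**Algebra (no assumed input).** Compound symmetry gives G = [[σ₁+σ, σ₁], [σ₁, σ₁+σ]], so Var(intercept) = Var(slope) = σ₁+σ. If concentration is multiplied by k, the slope is divided by k and its variance by k². An unstructured or diagonal G stays in its own family after this rescaling. A non-zero compound symmetry G does not, unless k = 1. Compound symmetry is not more economical either: it has two parameters, as variance components does.

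**Inputs for size.** The plan states no figure to reproduce; cohort sizes and doses are redacted and no variances are given. Assumed: 8 cohorts of 6 active and 2 placebo, 8 postdose ECG times, Cmax from about 2 to 200 µg/mL, intercept SD 6 ms, residual SD 5 ms, true slope 0.02 ms per µg/mL (so true ΔΔQTcF at 200 µg/mL is 0.02 × 200 = 4 ms), and slope SD 0 or 0.03. Fits are by REML, with intervals of ±1.645 SE rather than the KR2 degrees of freedom in the SAP code.

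**Why the intercept variance collapses.** A common SD of 6 in µg/mL would imply a between-participant spread of 6 × 200 = 1,200 ms at the top Cmax. The fit therefore drives the common variance towards the slope's scale. In mg/mL the same SD implies only 6 × 0.2 = 1.2 ms, so the constraint is milder.

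**One simulated data set (slope SD 0.03), ΔΔQTcF at 200 µg/mL with 90% CI:**

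| Structure | Unit | ΔΔQTcF, ms | −2RLL |
|---|---|---|---|
| Unstructured | all three | 6.67 (2.16 to 11.19) | 3238.0 |
| Variance components | all three | 6.88 (2.48 to 11.28) | 3239.6 |
| Compound symmetry | µg/mL | 1.50 (−4.22 to 7.23) | 3388.2 |
| Compound symmetry | ng/mL | 1.48 (−4.19 to 7.14) | 3389.5 |
| Compound symmetry | mg/mL | 7.41 (3.96 to 10.85) | 3244.1 |

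In µg/mL the intercept SD falls from about 5 ms to 0.07 ms. The fit is worse than variance components by 3388.2 − 3239.6 = 148.6 with the same number of parameters, yet the rule would accept it.

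**Repeated data sets, concentration in µg/mL** (475 with slope SD 0.03, 523 with slope SD 0). Cells show median SE, with coverage of the nominal 90% interval in brackets:

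| Quantity | Slope SD | Variance components | Compound symmetry | SE ratio |
|---|---|---|---|---|
| Slope | 0.03 | 0.0126 (0.869) | 0.0272 (0.891) | 2.2 |
| ΔΔQTcF at 200 | 0.03 | 2.81 (0.874) | 5.21 (0.905) | 1.9 |
| Placebo ΔQTcF | 0.03 | 1.56 (0.884) | 0.61 (0.480) | 0.39 |
| Slope | 0 | 0.0096 (0.893) | 0.0259 (0.901) | 2.7 |
| ΔΔQTcF at 200 | 0 | 2.42 (0.899) | 4.94 (0.902) | 2.0 |
| Placebo ΔQTcF | 0 | 1.57 (0.899) | 0.61 (0.516) | 0.39 |

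The median intercept SD under compound symmetry is 0.11 to 0.12 ms, against 5.9 to 6.0 ms under variance components. The placebo result can be checked by hand: the half-width is 1.645 × 0.61 = 1.00 ms and the empirical SD of the estimate is 1.60 ms, so coverage is P(|Z| < 1.00/1.60) ≈ 0.47.

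Medians are used because SEs under compound symmetry in µg/mL are skewed: in a separate 150 sets with slope SD 0.03 the mean SE for ΔΔQTcF was 14.08 ms, against 2.83 ms for variance components.

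**Range.** With top Cmax 396 µg/mL and residual SD 6 ms (about 40 sets per setting), the ΔΔQTcF SE was 3.2 to 3.4 ms under variance components and 7.8 to 8.5 ms under compound symmetry, a ratio of about 2.5. A further set of fits gave 2.4 to 3.0 ms against 7.5 to 8.0 ms.

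**The case against.** Several points on the other side stand.

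- **Validity of the main intervals.** A reader might infer that the slope and ΔΔQTcF intervals are invalid. In µg/mL they are not: coverage is 0.89 to 0.91 in the table, and a further check of 60 sets per setting found ΔΔQTcF coverage of 0.92 to 0.93 and mean estimates of 4.2 to 4.6 ms against a true 4.0. The harm there is lost precision. Undercoverage in µg/mL is confined to placebo ΔQTcF.
- **Unit contrast.** A reader might infer that any change of unit moves the result greatly. Between µg/mL and ng/mL the single data set barely moves. The large contrast needs mg/mL, which the documents never propose. In mg/mL with varying slopes, slope coverage falls to 0.76 and ΔΔQTcF coverage to 0.81.
- **Frequency.** A reader might expect the unstructured fit to fail often. Nothing in the documents shows this and no failure rate was measured. Protocol 1.3.1 and 8.2.3 give about eight postdose triplicate ECG times per IV participant, which is not sparse.
- **Stakes.** Protocol 9.3.5.1.1 treats this relationship as something to explore, Protocol 9.1 sets no formal hypotheses, and the primary endpoint is adverse events.

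The clause "Other covariance structures may be considered if deemed appropriate" allows the analyst to avoid compound symmetry but does not require it, and using it would make the choice after seeing the fit. None of this rescues compound symmetry as a structure for this G.

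**Conclusion.** Wrong as written; low severity. The equal-variance constraint and the dependence on unit are exact and need no assumed figure. The size rests on the assumptions listed: in µg/mL, slope and ΔΔQTcF intervals roughly 2 to 3 times as wide as under variance components at about nominal coverage, and a placebo ΔQTcF interval with coverage of about 0.5. Other cohort sizes, variances or exposures would change these figures. The defect has effect only if the unstructured model fails and compound symmetry then converges. The documents do not support calling the main ΔΔQTcF interval invalid in µg/mL, or saying that the fallback is likely to be used.

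**What to change.** Delete the compound symmetry bullet in SAP 10.6.5, so that the sequence runs from unstructured directly to variance components, which is already listed and does not depend on the unit. Leave the existing simplification order (interaction, then random slope, then random intercept) as it stands; this defect gives no reason to change it. Standardising concentration in advance would remove the dependence on unit, but equal variances would still be arbitrary, so deletion is the better remedy. The cost is one line in the SAP, with no effect on data collection, sample size or the primary analysis.

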1.3. Schedule of Activities (SoA)

1.3.1. Part A: Single-Ascending Dose of LY3872386 in Healthy Participants

1.3.1. Part A	ı. omgr	-ASC	enaing D	Part A: S									Particip	ants					
Procedures / Assessments	Screen	ning	Treatment Period									E D	Comments						
Visit Number	V1		l	•	V2					V 801	V 802	V 803	V 804	V 805	V 806	V 807	V 808		
Study Day	C	C																	
Informed consent	X																		
Review/confirm I/E criteria	X	X																	
Admission to CRU		X																	CUI
Randomization			P																
Discharge from CRU									X										
Outpatient visit										X	X	X	X	X	X	X	X	X	
Clinical Assessments	3																		
Complete medical history	X																		
Review AEs	X	X	P	X	X	X	X	X	X	X	X	X	X	X	X	X	X	X	
Concomitant medications	X	X	P	X	X	X	X	X	X	X	X	X	X	X	X	X	X	X	
Substance use (alcohol and tobacco use)	X	X											X				X	X	CCI
Physical examination	X	X											X		X		X	X	

]	Part A: S	ingle	-Asce	ending	g Dose	of LY	387238	6 in H	ealthy I	Particip	ants					
Procedures / Assessments	Screei	ning	Treatment Period							Follow-up									Comments
Visit Number	V1			V2					V 801	V 802	V 803	V 804	V 805	V 806	V 807	V 808			
Study Day	C	C																	
Weight	X	X															X	X	
Height	X																		
Vital signs	X	X	X	X	X	X	X	X	X	X	X	X	X	X	X	X	X	X	
ECGs	X		P	X	X		X		X		X		X		X		X	X	
Chest x-ray, if indicated (posterior-anterior view)	X																		
QuantiFERON®-TB Gold test or TST	X																		
IP administration			X																
Laboratory Assessm	ents	1								 									
Serologies, syphilis, and FSH	X																		
Thyroid-stimulating hormone, including T3/T4 tests		X															X	X	OOI
Serum immunoglobulins	X		P						X		X		X		X		X	X	

			P	art A: Si	ngle-	Asce	nding	g Dose	of LY	387238	6 in He	ealthy I	Particip	ants					
Procedures / Assessments	Screen	ning		Treat	men	t Peri	iod						Follo	ow-up				E D	Comments
Visit Number	V1			V	2					V 801	V 802	V 803	V 804	V 805	V 806	V 807	V 808		
Study Day	C																		
CCI			<1-, 15-, 120-, and 240-min post injection	24 hr	X	X			X		X		X						CCI
Urinary drug screen (including ethanol breath test)	X	X																	
Pregnancy test	X	X															X	X	
Clinical chemistry	X	X	P	X	X		X		X	X	X	X	X	X	X	X	X	X	
Bedside glucose monitoring		X	P and 12 hr	24 hr and 36 hr					X										
Fasting lipid panel			P										X					X	
Hematology	X	X		X	X		X		X		X	X	X	X	X	X	X	X	
Hemoglobin A1c	X	X											X				X	X	

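### The concentration-QTc fallback may end with no participant-level term; if that step were reached, the nominal 90% CIs would under-cover (low priority)

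*SAP*

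**What the plan says.** SAP 10.6.5, Concentration-QTc Analysis (Part A only), models change from baseline in QTcF on time-matched LY3872386 concentration. Treatment, PK profile day, time, their interaction and centred baseline are fixed effects, "and a random intercept and concentration slope per participant". Residuals "are Gaussian distributed with mean 0 and variance r". The only participant-level line in the example code is "random intercept conc / subject=subjid type=un".

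If the unstructured covariance fails, compound symmetry and then variance components are tried. If the model still does not converge, the day-by-time interaction goes first, "followed by the random effects for slope, followed by intercept, will be removed until convergence is achieved". The next sentence is a general allowance: "Other covariance structures may be considered if deemed appropriate".

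On output, "The LY3872386 concentration slope and corresponding 90% CI will be reported", together with predicted ΔQTcF and ΔΔQTcF at each dose level's geometric mean Cmax, also with 90% CIs. The section extends a similar analysis to RR, HR, PR and QRS.

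**The concern.** Each Part A participant contributes several post-dose ECG records, and active versus placebo is a between-participant contrast. The random intercept and slope are the only terms that let records from one participant be correlated. Once both are removed, every record counts as independent information, and the between-participant contrast is judged against the number of rows rather than the number of participants.

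Non-convergence is a numerical event. It is not evidence that participants do not differ. A rule that responds to it by assuming independence can report intervals labelled 90% that do not have 90% coverage. At stake is the accuracy of the uncertainty attached to the slope and to the Cmax predictions.

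**Working it through.** The documents give no sample size, ICC or coverage figure for this analysis, so there is no stated figure to reproduce.

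**Step 1: records per participant.** The Part A schedule (Protocol 1.3.1) has the row "ECGs X P X X X X X X X X X".
- After the Day 1 predose mark (P) come four inpatient marks, then V802, V804, V806, V808 and the early-discontinuation visit.
- Under SAP 10.6.5 the last scheduled follow-up visit is not taken in triplicate, so V808 drops out.
- SC cohorts: 4 + 3 = 7. IV cohorts add the Day 1 post-dose ECG in Protocol 8.2.3: 7 + 1 = 8.
- Triplicates are averaged first, so each time point gives one row.
- These are scheduled maxima. Concentrations below the quantification limit are set to missing in the active arms. The Day 1 wording in Protocol 8.2.3 could also be read as allowing 9 for IV.

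**Step 2: how large the residual correlation can be.** Baseline is a covariate. Suppose baseline and all post-dose values of a participant have equal variance (set to 1) and common correlation ρ. Given baseline:
- residual variance = 1 − ρ²
- residual covariance = ρ − ρ²
- residual ICC = ρ(1 − ρ) / [(1 − ρ)(1 + ρ)] = ρ/(1 + ρ)

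This cannot exceed 0.5. A residual ICC of 0.25 corresponds to ρ = 1/3, and 0.05 to ρ = 0.05/0.95 = 0.053.

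**Step 3: design effect for a between-participant contrast.** With m rows per participant, DEFF = 1 + (m − 1) × ICC. The naive SE is too small by √DEFF, and non-coverage is 2 × [1 − Φ(1.645/√DEFF)].

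| ICC | m | DEFF | √DEFF | Non-coverage |
|---|---|---|---|---|
| 0 | 7 or 8 | 1.00 | 1.00 | 10.0% |
| 0.05 | 7 | 1.30 | 1.14 | 14.9% |
| 0.05 | 8 | 1.35 | 1.16 | 15.7% |
| 0.25 | 7 | 2.50 | 1.58 | 29.8% |
| 0.25 | 8 | 2.75 | 1.66 | 32.1% |
| 0.5 | 7 | 4.00 | 2.00 | 41.1% |
| 0.5 | 8 | 4.50 | 2.12 | 43.8% |

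**Step 4: simulation with the SAP's type of fixed effects and no random effects.** Assumptions not in the documents: 8 cohorts; 6:2 or 8:2 active to placebo in each; relative doses 1 to 300; 10-day half-life; exchangeable correlation; no drug effect. Non-coverage of the nominal 90% CI, across the treatment term, the concentration slope and ΔΔQTcF at the highest Cmax:
- ICC 0: 9-11%
- ICC 0.05: 13-17%
- ICC 0.25: 26-32%
- ICC 0.5: 37-44%

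The ICC 0 row shows that the calculation itself is calibrated. The other rows agree with Step 3, with the slope at the lower end because it also uses within-participant information.

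**Step 5: how likely the step is.** Steps 3 and 4 apply the intercept-free fit to every data set. In a comparable set-up (600 replicates per setting), the random-intercept-only model was fitted by REML instead. The optimiser never failed. The participant variance was estimated at zero in 0% of replicates at ICC 0.25 and 0.5, in 4% at ICC 0.05 and in about 52% at ICC 0. The data were correctly specified and Gaussian, and the optimiser was not PROC MIXED.

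**The case against.** The strongest reply is that the rule would hardly ever get this far. Three covariance structures, removal of the interaction and removal of the slope all come first, and then a model with only two variance parameters must fail. Step 5 found no such failure, and zero variance estimates arose mainly where the true correlation was near zero and little coverage would be lost. This stands: the percentages in Step 4 are conditional on the step being reached and do not forecast what the trial will report.

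The allowance for other covariance structures already permits a valid rescue. That also stands, but it is discretionary, names no structure and sets no minimum.

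Four stronger readings are tempting, and none is supported:
- **That an upper 90% limit from this model will be used to exclude a QTc effect.** Neither document sets a QTc threshold for the model. Protocol 9.3.5.1.1 says the relationship will be explored, Protocol 9.1 sets no formal hypotheses, and SAP 10.6.15 plans no inferential safety analysis. The individual QTc criteria in Protocol 7.1.3.1 and the categorical QTcF summaries in SAP 10.6.5 do not depend on it.
- **That rows are correlated by construction because they share a baseline.** With baseline as a covariate, change and raw post-dose value leave the same residuals. The correlation that matters is whatever participant difference persists afterwards, which is an empirical matter.
- **That five ECG parameters give a material chance of reaching the step.** No failure probability is available for any of them.
- **That the intercept-free interval is always narrower than one from a model that keeps the intercept.** For the slope, the ratio of the SE that allows for the correlation under the retained-intercept model to the naive SE ran from 0.83 to 1.40 over scenarios with ICC 0.2 to 0.7 (0.7 lies above the Step 2 ceiling). The defect is under-coverage of the fallback estimator's own error.

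**Conclusion.** The point holds as a conditional defect. When triggered, the SAP's stated rule ends in a model that ignores repeated measurement within participants. If participant differences then persist after baseline adjustment, the 90% CIs for the slope and for ΔQTcF and ΔΔQTcF at Cmax under-cover, to the extent shown in Step 4. An ICC of 0.5 is the ceiling under exchangeable correlation with baseline as a covariate; with no residual correlation there is no loss.

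The size rests on assumed cohort sizes, doses, half-life and ICC. A reader might infer that the trial's QTc intervals will be wrong. The documents do not support that, because the planned model and every earlier fallback keep a participant-level term. Since the step should be rare and the analysis is exploratory, this is a low-priority correction. It is still worth making, because the prescribed endpoint is invalid and the allowance that follows it sets no floor.

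**What to change.** In SAP 10.6.5, stop the reduction sequence at the random-intercept model and state that a participant-level term is kept in every reported fit. If the random-intercept model does not converge:
1. Rescale concentration and refit.
2. If it still fails, fit the same fixed effects with REPEATED / SUBJECT=subjid TYPE=CS, or use participant-clustered standard errors (EMPIRICAL option).
3. Do not report a fit with no participant-level term.

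Apply the same floor to RR, HR, PR and QRS. The cost is a sentence or two of SAP text and a line of code, with no new data. Results are unchanged unless the last step would have been reached, in which case the intervals may be wider.

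### The concentration-QTc code in SAP 10.6.5 fits straight lines in day and hour where the model text has categorical time, which can bias ΔΔQTcF at Cmax; the placebo and ΔQTcF rows also lack time coefficients

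*SAP*

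**What the plan says.** The text of SAP 10.6.5 (Concentration-QTc Analysis, Part A only) lists "PK profile day, time (nominal time postdose), and the interaction between PK profile day and time as fixed effects". In the formula these terms are indexed by level: θ3 by day k, θ4 by hour l, and θ5 by both. The text then refers to a "fixed effect associated with categorical hours postdose". The definition of the day term seems to have been lost when the PDF was read, so the categorical reading of day rests on its index. For hour it is explicit.

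The example SAS code has the CLASS statement "class trt(ref='0') time subjid" and the MODEL statement "model ΔECG = basec trt day hour day*hour conc / cl alpha=0.1 ddfm=kr2". The placebo prediction is "estimate 'PBO' intercept 1 trt 0 1 conc 0/ cl alpha=0.1". The ΔQTcF row has the same form, with the active treatment level and Cmax as the concentration. The ΔΔQTcF row has only the treatment contrast and Cmax.

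The SAP wants ΔQTcF and ΔΔQTcF at the geometric mean Cmax of each dose "for the last PK profile day along with the corresponding 90% CIs". It also says that RR, HR, PR and QRS will be analysed in a similar way.

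**The concern.** PROC MIXED treats any model variable that is not in CLASS as numeric. Run as written, the code estimates one slope for `day`, one for `hour` and one for their product. The text calls for a separate effect at each level. The two are different models, and the SAP has no rule for which prevails.

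This matters more in a single-dose study than it might elsewhere. Within each active participant, concentration is largely a function of time since dose. Any QTcF pattern over time that both arms share, such as time of day or inpatient versus outpatient conditions, has to be removed by the time terms. What they leave behind is correlated with concentration, and the slope can pick it up. The slope then feeds ΔΔQTcF at Cmax.

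Part A carries the only concentration-QTc analysis. ECGs in Parts B and C are single by default (Protocol 8.2.3) and are presented only if collected in triplicate (SAP 10.6.5).

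**Working it through.** The documents give no figure to reproduce, so the check has three steps.

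**1. Text against code**

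| Term | Model text | Code |
|---|---|---|
| Day | one effect per level k | numeric slope |
| Hour | categorical, one effect per level l | numeric slope |
| Day by hour | one effect per pair | product of two numerics |
| `time` | not a separate term | in CLASS, absent from MODEL |

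**2. Can the ESTIMATE rows be computed?** A row is estimable only if it lies in the row space of the design matrix.

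- `day` constant at 1 (one PK profile day): `day` equals the intercept column in every record. A row with intercept 1 and `day` 0 is not in the row space, so the placebo and ΔQTcF rows are non-estimable.
- `day` numeric and varying (study day): both rows are estimable, but the omitted coefficients are zeros, so they predict at day 0, hour 0. That is not the last PK profile day.
- Time categorical, as in the text: both rows are non-estimable until time coefficients are added.
- The ΔΔQTcF row is estimable in every case, because the time terms cancel.

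**3. Bias in ΔΔQTcF with no true drug effect.** Let f be a time pattern of 1 ms common to both arms. The expected generalised least squares estimate is b = (X′V⁻¹X)⁻X′V⁻¹f. The bias is b(active) − b(placebo) + b(conc) × Cmax.

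From the documents: eight cohorts and their routes (Protocol 4.1 and Table KMAA.1); a single dose on Day 1; a Day 1 postdose ECG at about 6 h in IV cohorts only and one at about 24 h in all (Protocol 8.2.3); IV and SC pooled.

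Assumed, because redacted or not given:
- active to placebo 6:2 in Cohorts 1 to 5 and 9:3 in Cohorts 6 to 8
- relative doses 1 to 80
- further ECGs at 48, 96, 144, 336, 672 and 1344 h
- terminal half-life 5 or 10 days
- intercept SD 5 ms, residual SD 6 ms, and a small random slope

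Bias at the top-dose Cmax, in ms per 1 ms of time effect (range over the two half-lives):

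| Coding | Shift at 6 h only | Shift through 144 h | Shift in first 24 h |
|---|---|---|---|
| (a) `day` = 1, `hour` = hours since dose | 0.58 to 0.69 | 0.37 to 0.49 | 0.72 to 0.93 |
| (b) `day` = study day, `hour` = hours since dose | 0.00 | about −0.01 | 0.14 to 0.24 |
| (c) `day` = study day, `hour` = hour within day | 0.00 | 0.34 to 0.47 | 0.31 to 0.45 |
| Categorical time point | 0.00 | 0.00 | 0.00 |

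The zeros for a 6 h effect under (b) and (c) are exact. Under (b), `hour` − 24 × (`day` − 1) is 6 − 0 = 6 at the 6 h ECG, 24 − 24 = 0 at 24 h on Day 2, and 1344 − 24 × 56 = 0 on Day 57. The numeric terms therefore contain a 6 h indicator. Under (c), `hour` is itself non-zero only at 6 h. Under (a), `day` and the product add nothing, and one straight line over 1344 h has to describe all time effects.

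The bias has the sign of the time effect in all but the negligible (b) entry. A 5 ms effect gives from about 0 to 5 × 0.93 ≈ 4.7 ms, against a standard error of ΔΔQTcF of about 2.3 to 2.5 ms in this design. Other assumed dose spacings with `day` constant gave about 0.22 to 0.61 ms per ms.

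**The case against.** The strongest reply is that the specification is right and only the illustration is wrong. The code is offered as examples and contains placeholders, and a competent programmer would notice that `time` is declared but not modelled. That limits the fault to a mismatch between text and code, and it is why the remedy is small. It does not remove the fault, because the SAP also says this is the code that will be used, and as written it runs a different model.

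A second reply is that other outputs do not depend on this coding: summaries by time point, counts above QTcF thresholds, and separate two-sample comparisons at each time through 24 h. The protocol (9.3.5.1.1) says only that the relationship will be explored, and the primary endpoints are adverse events. This is fair and lowers the stakes. However, the planned model check plots residuals against concentration, not time, and the fitted slope may already have absorbed the pattern.

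A reader might infer that a diurnal dip at 6 h must be read as a negative drug effect and so could hide prolongation. The documents do not support that. It requires `day` to be constant, and under either study-day coding a 6 h effect causes no bias. A reader might also infer that all three prediction rows are faulty, but the ΔΔQTcF row is correct.

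**Conclusion.** The concern holds in this form: the code does not fit the model that the text specifies, and two of the three prediction rows do not deliver the stated output. Both follow from reading the SAP and need no assumption.

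That ΔΔQTcF at Cmax can be biased is also established, but not by how much. The range of about 0 to 0.9 ms per ms of shared time effect rests on assumed doses, cohort sizes, ECG times and half-lives, on the shape of the time effect, and on a coding of `day` and `hour` that the SAP leaves open. No time effect of any particular size can be read from the documents. The two faults are separate: linear time is the only source of bias in ΔΔQTcF, while the missing coefficients affect only the placebo and ΔQTcF rows. The point should be corrected before the analysis is programmed. It is not evidence that the QT conclusion will be wrong.

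**What to change.** 1. Fit nominal time postdose as one categorical factor with a distinct level for each scheduled ECG time point. The simplest way is to keep the CLASS statement, define `time` as nominal hours since dose, and replace `day hour day*hour` in MODEL by `time`, giving `basec trt time conc`. Putting both `day` and `hour` in CLASS is equivalent if every ECG time point keeps its own level.
2. Do not use hour within day alone. It merges the follow-up visits into one level, and under the assumed design the bias for an inpatient-period effect is then about 1.3 ms per ms.
3. Add coefficients for a stated target time point, or equal weights over time points, to the placebo and ΔQTcF rows. Adding variables to CLASS without this leaves those rows non-estimable. Leave the ΔΔQTcF row as it is.
4. Replace the reference to the last PK profile day with that stated time point, and bring the formula's day and hour indices into line.
5. Make the same change for RR, HR, PR and QRS.

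The cost is a few lines of code and text and a few degrees of freedom. In the assumed design the standard error of ΔΔQTcF rises from 2.39 to 2.54 ms (5-day half-life) or from 2.31 to 2.40 ms (10-day) relative to coding (a).
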